### **I. Study Aims**

The current study will assess the safety and efficacy of an enteral formulation of the opioid antagonist naloxone in prevention of post-operative ileus and opioid induced constipation.

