### **I. Study Design**

This is a prospective, historically controlled observational trial of enteral naloxone use in patients admitted for spinal fusion surgery and receiving opioids for pain management.

Primary outcome: Time to first bowel movement (hours)

Secondary outcomes:

- Hospital length of stay
- Incidence of post-operative ileus. Post-operative ileus will be diagnosed through a combination of clinical exam and radiographic (X-ray) findings
- incidence of post-operative constipation (defined as 3 days without a bowel movement)
- average numerical pain scale (Adult Nonverbal Pain scale or Visual Analog Scale) on post-operative days 0, 1, 2, and 3
- average daily opioid requirement on post-operative days 0, 1, 2 and 3 (morphine equivalents)
- number of naloxone doses administered
- average number of daily bowel movements,
- number of medication escalations required (defined as use of an as needed laxative medication or addition of a new order for a laxative medication)
- Incidence of adverse effects
- Incidence of study drug discontinuation

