### Screening procedures

Patients will be screened at the pre-operative clinic visit based on the inclusion and exclusion criteria.

Historical controls will be identified by a report of patients undergoing spinal fusion procedures

identified via ICD9 codes in the previous 3 years. ICD-9 codes include a short fusion surgery (81.06, 81.62) with 3 or fewer vertebral body segments, long fusion surgery (81.63, 81.64), more than 4 vertebral segments, anterior approaches (81.06) and posterior approaches (81.07) in the thoracic and lumbar spine. The historical controls will be matched to active participants based on age, gender, Charleston co-morbidity index, complexity of surgery, and duration of surgery.

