### Study Assessments and Activities

All patients will undergo the scheduled operation per routine. Post operatively, all usual medications for pain control and bowel movements will be ordered according to institutionally approved and reviewed post-operative order sets. All home medications will also be reconciled and restarted as deemed clinically appropriate by the interdisciplinary care team. Oral naloxone 4 mg enterally every 8 hours will be initiated on post-operative day 1 at 0900. Study drug will be discontinued as described in the study protocol, after 48 hours, or upon discharge whichever is sooner.

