#### Analysis Plan

Two different approaches will be used for the primary aim. First, a paired *t*-test will be used to estimate the mean difference in hours to first feces between the active cohort and historical control cohort. For this analysis, the origin of time for both groups is start of surgery. If necessary, a Wilcoxon signed ranks test will be used to compare the two distributions.

A second approach will compare the instantaneous rates of bowel movements between the active and control cohorts using a Frailty survival model that allows for clustering of patients within their matched strata. In this analysis, control patients who required treatment for ileus will be censored at the time of such treatment, and active patients who require an additional treatment beyond receipt of naloxone will be censored at the time of such treatment. All patients who do not achieve BM by 120 hours will also be censored. Hours to first feces for both groups will be start of surgery. While we assume there is no immortal time bias between start of surgery and receipt of naloxone for the active cohort, a conditional landmark method may be used to account for the amount of hours between surgery and receipt of naloxone. The proportional hazards assumption for all predictors will be tested using Martingale residuals as described by Lin, Wei, and Ying.

Regarding the secondary aims, a linear mixed effects model will be used to compare LOS between the two groups. A generalized linear mixed effects model will be used to compare the two groups on all other secondary outcomes. In these models, random intercepts will be allowed for each case-control matched strata in order to account for the correlation between cases and controls based on age, gender, Charleston co-morbidity index, and operation time under anesthesia.

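### Opioid exposure is neither matched nor specified as a covariate for time to first bowel movement, although pre-dose opioid use on post-operative day 0 is a planned data item

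*Combined protocol and SAP*

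**What the plan says.** The Study Aims name the target as use of the "opioid antagonist naloxone in prevention of post-operative ileus and opioid induced constipation". Study Design describes a prospective cohort set against historical controls.

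**Matching.** Under Screening procedures, controls are "matched to active participants based on age, gender, Charleston co-morbidity index, complexity of surgery, and duration of surgery". The Analysis Plan restates the factors when it describes the "correlation between cases and controls based on age, gender, Charleston co-morbidity index, and operation time under anesthesia", this time without complexity of surgery. Neither list has an opioid variable.

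**Primary analysis.** There are two approaches. In the first, "a paired *t*-test will be used to estimate the mean difference in hours to first feces", with a signed-rank test as fallback. The second compares BM rates "using a Frailty survival model that allows for clustering of patients within their matched strata". No adjustment covariate is named for either. The only hint of one is the sentence "The proportional hazards assumption for all predictors will be tested using Martingale residuals", and those predictors are not listed.

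**Opioid data.** Study Design lists "average daily opioid requirement on post-operative days 0, 1, 2 and 3 (morphine equivalents") as a secondary outcome only. Study Assessments and Activities starts naloxone at 0900 on post-operative day 1, so day 0 use precedes it. The same section says "All home medications will also be reconciled and restarted as deemed clinically appropriate by the interdisciplinary care team".

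**Eligibility.** Participants need an opioid-containing pain plan, with no condition on dose or previous use. Controls are found by procedure code over the previous three years, with no opioid condition stated.

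**The concern.** Opioid load is part of the condition under study, so it is a plausible cause of a late first BM. If controls and participants differ in opioid load, part of the difference in time to BM, constipation or ileus will reflect that load and not naloxone.

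The matching factors may balance surgical opioid need in part. They do not address opioid use before admission, or any change in analgesic practice between the historical window and the trial. The frailty term allows for correlation within matched strata, but it does not remove a systematic difference between cohorts in an unmatched factor. Meanwhile the plan collects a measure of opioid use that naloxone cannot have affected, and uses it only as an outcome.

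**Working it through.** **1. The plan's power figure.** Inputs from Power Analysis: rates 0.160 and 0.241 per day, 150 per cohort, 5 days, hazard ratio (HR) 1.508, two-sided alpha 0.05.

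- Expected events: 150 × (1 − exp(−0.160 × 5)) + 150 × (1 − exp(−0.241 × 5)) = 82.6 + 105.0 = 187.6.
- Power (Schoenfeld): Φ(ln 1.508 × √187.6 / 2 − 1.96) = Φ(2.814 − 1.96) = 0.803.

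The plan states 80.1%, so its figure reproduces and is not in dispute. The calculation makes no allowance for confounding.

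**2. Illustration of bias, on assumed inputs.** The documents give neither an opioid distribution nor an association between opioid dose and BM. Assume that low-opioid patients have a BM rate of 0.20 per day and high-opioid patients 0.20 × r, with no naloxone effect. In a cohort with high-opioid share p, the proportion without a BM at time t is

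S(t) = (1 − p) exp(−0.20 t) + p exp(−0.20 r t).

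The HR is the average proportional-hazards ratio over 5 days with 150 per cohort. With D expected events and z = ln(HR) × √D / 2, the rejection rate is Φ(z − 1.96) + Φ(−z − 1.96).

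| r | High-opioid share, controls v naloxone | D | Spurious HR | Rejection at nominal 5% |
|---|---|---|---|---|
| 0.8 | 40% v 30% | 181 | 1.02 | 5.3% |
| 0.6 | 40% v 30% | 171 | 1.05 | 6.2% |
| 0.5 | 40% v 30% | 165 | 1.07 | 7.1% |
| 0.6 | 50% v 30% | 168 | 1.10 | 9.9% |
| 0.5 | 50% v 30% | 161 | 1.14 | 13.5% |
| 0.5 | 30% v 50% | 161 | 0.88 | 13.5% (against naloxone) |

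Hand check of the fifth row from the rates at time zero: (0.7 + 0.3 × 0.5) / (0.5 + 0.5 × 0.5) = 0.85 / 0.75 = 1.13. Depletion of the faster patients over 5 days moves this to 1.14.

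**3. Effect on power if the imbalance is reversed.** With r = 0.5 and 30% v 50%, the time-zero ratio is 0.75 / 0.85 = 0.882. A true HR of 1.508 then appears as 1.508 × 0.882 = 1.33, and power is Φ(ln 1.33 × √187.6 / 2 − 1.96), or about 50%.

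These calculations ignore matching, which may reduce the imbalance. Wider assumed imbalances would give larger figures.

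**4. Whether day 0 use can enter the model as planned.** Both primary approaches start time at surgery, so day 0 opioid use accrues after the origin. A patient with an early BM would be adjusted for opioid given after the event. Day 0 use becomes a proper baseline covariate only if time starts at the first-dose time point, which the optional landmark method in the Analysis Plan would allow.

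**The case against.** The case for leaving the plan alone has several parts.

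- **Matching may already cover much of it.** The background names anterior approach and duration of surgery as ileus risk factors, and the matching includes duration and complexity. This stands in part: it may balance surgical opioid need, but not previous use or changes in practice.
- **Covariates may be intended.** The reference to predictors in the proportional-hazards check suggests that some were foreseen. A reader might infer that the plan decided against opioid adjustment. The documents do not support that; the gap is that none is specified.
- **An imbalance would be visible.** Day 0 morphine equivalents are compared between cohorts as a secondary outcome. That is true, but seeing an imbalance does not correct for it, and adjusting only after seeing it would be a post-hoc choice.
- **The magnitude is assumed and may be negligible.** This stands. At the mild end, rejection is 5.3%, and no spurious HR in the table comes near 1.508.

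A reader might also infer that home opioid and laxative use is already recorded for the study. It is not stated to be: the plan describes reconciliation of home medications as post-operative care, and says nothing of study data capture or of controls. The point stands on day 0 morphine equivalents alone.

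**Conclusion.** The point holds as a specification gap in a non-randomised comparison: no opioid variable is matched, and none is specified as a covariate for time to first BM, although a pre-dose measure is planned.

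The size of any bias is unknown. On the assumptions shown (r of 0.5 to 0.8, high-opioid shares differing by 10 to 20 percentage points), the spurious HR lies between about 0.88 and 1.14, with rejection up to about 13.5%.

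Two stronger readings are tempting and unsupported. One is that the bias favours naloxone. That requires controls to have had the higher opioid load, which no document says; the reverse would hide a real effect. The other is that a difference could not be attributed to naloxone at all. The illustrative biases are too small, and too dependent on assumed inputs, for that. A change to the plan is advisable, with medium confidence.

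**What to change.** In the Analysis Plan:

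1. Specify the landmark analysis that is now optional: time starts at 0900 on post-operative day 1 in both cohorts, among patients with no BM by then. Include day 0 morphine equivalents as a fixed covariate in that frailty model.
2. Include the same covariate in the constipation and ileus models.
3. Add home opioid use and home laxative use (each yes/no) as baseline covariates, abstracted from the charts of both cohorts as new data fields. They precede surgery, so they also suit the analysis timed from surgery.
4. State that opioid use on days 1 to 3 will not be adjusted for, because naloxone may change it.
5. Describe the paired t-test or signed-rank result as unadjusted for opioid exposure, since those tests take no covariates.

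**Cost.** The change needs revised wording, two new chart fields and no new patients or procedures. Patients with a BM before the landmark drop out of that analysis. As a rough guide, if the landmark falls about one day after surgery and the plan's control rate held constant from the start, that would be 1 − exp(−0.160 × 1) = 15% of a cohort; both conditions are assumptions. Day 0 totals, as listed, also leave out opioid given on day 1 before 0900. Including it would need a further extraction window in both cohorts.

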### Study Intervention

Active study agents: Naloxone

Blinding/labeling/preparation of agents: No blinding is required in this study. The study drug will be prepared, unit dose labelled, and patient labelled according to institutional protocols.

Storage: Secured at room temperature in the central pharmacy then dispensed as a patient specific supply and stored at room temperature the automated dispensing cabinet. No more than a 24 hour supply will be dispensed at any given time.

Administration: 4 mg of a 1 mg/ml oral solution administered enterally (oral, nasogastric, orogastric, gastrostomy, or jejunostomy) every 8 hours for 48 hours

### Toxicities and guidelines for adjustments

Potential adverse effects associated with the use of enteral naloxone have been associated with abrupt reversal of opioid activity with the most uncomfortable or dangerous of these being antagonism of central opioid activity and loss of pain control. Additional adverse effects include nausea, vomiting, diarrhea, hypertension, tachycardia, diaphoresis, and mental status changes. Patients will be monitored for adverse effects via routine vital signs, pain score, and neurological assessment every 1 – 4 hours and evaluation for emesis, bowel movements, and diaphoresis. Study drug will be discontinued in patients who meet any three of six criteria within 1 hour of study drug administration:

1. Heart rate increases > 20 beats per minute for > 5 minutes
2. Respiratory rate increases to > 20 breaths per minute
3. Diaphoresis
4. Pain score increases by > 50%
5. Emesis
6. Diarrhea (defined as > 1 large, liquid bowel movement within 1 hour)

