**I. Analysis Plan**

Power Analysis

Power estimates for this study were based on prior work by Lee et al. In their study, patients were randomly assigned to receive morphine with naloxone or morphine without naloxone. They found that those who received naloxone had a shorter time to first postoperative passage of flatus ( $M = 51.9$ hr,  $SD = 16.6$ hr) versus control ( $M = 87.0$ hr,  $SD = 19.5$ hr). Similarly, the authors found that time to first feces was faster in the naloxone cohort ( $M = 95.3$ hr,  $SD = 25.0$ hr) than control group ( $M = 132.9$ hr,  $SD = 29.4$ hr). However, their study duration was exceedingly long with a maximum duration of approximately 160-180 hours. One goal of this study is to estimate the effect of naloxone on time to first feces within the first 120 hours (5 days) following treatment. In this study, patients who require a second intervention or who do not experience flatus or feces by Day 5 will be censored.

The null hypothesis is that the bowel movement (BM) rate is identical in the two groups (control and naloxone). Power is computed to reject this null hypothesis. Computation of power is based on a hazard ratio of 1.508. Specifically, it assumes instantaneous BM rates of 0.160 for the control group versus 0.241 for the naloxone group. This is equivalent to a median time of no BM of 4.34 days for the control group versus 2.879 days for the naloxone group. At 5 days, it is hypothesized that 45% of the control cohort versus 30% of the naloxone cohort will require a second intervention because they have not experienced a BM.

With a total of 150 patients entered into the naloxone group and a total of 150 historical controls, the study will have power of 80.1% to yield a statistically significant result. The

criterion for significance (alpha) is set at 0.050, and the test will be 2-tailed meaning an effect in either direction will be interpreted.

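### The pain criterion in the stopping rule is a purely relative rise, so it cannot be met from two-thirds of the scale maximum upward, and from a score of 0 the text leaves it open

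*Combined protocol and SAP*

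**What the plan says.** In the combined protocol and SAP, the section Toxicities and guidelines for adjustments gives the stopping rule: "Study drug will be discontinued in patients who meet any three of six criteria within 1 hour of study drug administration". The six criteria are heart rate, respiratory rate, diaphoresis, pain, emesis and diarrhea. Criterion 4, the only one on pain, reads "Pain score increases by > 50" per cent. The same section describes the adverse effects of enteral naloxone as linked to abrupt opioid reversal, "the most uncomfortable or dangerous of these being antagonism of central opioid activity and loss of pain control".

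The plan does not say which earlier score the rise is measured from, and it gives no absolute rise or severe-pain level as an alternative. The stopping rule names no scale. The Study Design section lists as a secondary outcome the "average numerical pain scale (Adult Nonverbal Pain scale or Visual Analog Scale) on post-operative days 0, 1, 2, and 3", without numeric ranges. Study Assessments and Activities and the Safety Monitoring Plan add no other pain-based stop.

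**The concern.** A percentage change on a bounded scale behaves differently at different starting points. From a low score, a one-point rise can exceed 50%. From a high score, even a rise to the worst possible pain cannot. The criterion is therefore closed to the patients who already have the most pain, although it addresses a hazard that the protocol itself puts among the worst effects of the drug.

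Take two patients on a 0-10 scale who both have emesis and diaphoresis after a dose. One goes from 4 to 7 and must stop. The other goes from 7 to 10, the same three-point rise to a worse level, and the rule does not require stopping. The plan gives no reason for the difference. There is also a reporting consequence: the Safety Monitoring Plan defines a serious adverse event by the need to discontinue study drug, and discontinuation is a listed secondary outcome.

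**Working it through.** **Plan's own figure.** The stopping rule has no numerical justification to reproduce. The one computed design figure is the power of 80.1% (Power Analysis), where "Computation of power is based on a hazard ratio of 1.508". With 150 per group and 45% and 30% without a bowel movement at 5 days, expected events are 150 × 0.55 + 150 × 0.70 = 187.5. Schoenfeld's formula gives Φ(√(187.5/4) × ln 1.508 − 1.96) = Φ(0.852) = 80.3%, which agrees. Nothing below depends on it.

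**Inputs.** From the protocol: a strict inequality at 50%, and three of six criteria. Assumed: scores are whole numbers on 0-10 or 0-100, because the documents give no range, and the comparison score is the last one before the dose.

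**Ceiling.** From pre-dose score b on a scale with maximum M, the largest possible relative rise is (M − b)/b. It exceeds 0.5 only if b < M/1.5 = 2M/3. At exactly 2M/3 it equals 50%, which fails the strict inequality. This result holds for any M.

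**Current rule on 0-10** (post-dose score s must exceed 1.5b):

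| Pre-dose score | Largest possible rise | Smallest score that counts |
|---|---|---|
| 0 | undefined | not settled |
| 1 | 900% | 2 |
| 2 | 400% | 4 |
| 3 | 233% | 5 |
| 4 | 150% | 7 |
| 5 | 100% | 8 |
| 6 | 66.7% | 10 |
| 7 | 42.9% | none |
| 8 | 25% | none |
| 9 | 11.1% | none |
| 10 | 0% | none |

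On 0-100, scores 1-66 can meet the criterion and 67-100 cannot.

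**Other reading of 50%.** If it meant half the scale range, a rise of more than M/2 would be needed. That is impossible from M/2 upward, so the blocked range would be wider.

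**Score of 0.** As a percentage, the change divides by zero. Read as s > 1.5b, any rise from 0 counts. The text does not choose between these readings.

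**Proposed wording on 0-10** (more than 50%; or at least +3; or, from 7 upward, at least +2 or to 10). The smallest qualifying scores from 1-5 stay at 2, 4, 5, 7 and 8. From 6 the smallest becomes 9 instead of 10. Upward moves from 7-9 number 3 + 2 + 1 = 6. The current rule counts 0, and the new wording counts 4: 7 to 9, 7 to 10, 8 to 10 and 9 to 10.

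**Proposed wording on 0-100** (+30; or, from 67 upward, +20 or to 100). Upward moves from 67-99 number 33 + 32 + … + 1 = 561, and the current rule counts 0. From 67-80 the new wording counts 14 + 13 + … + 1 = 105. From 81-99 it counts one each, 19. The total is 124 of 561 (22%). Triggers at 1-59 are unchanged: from 59, more than 50% needs a score above 88.5, so 89, which is already +30. The required score falls from 96 (pre-dose 66) to 87 (pre-dose 67), a step that the investigators may want to smooth.

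**The case against.** The strongest reply is that little turns on this. Pain alone never stops the drug, and three of the other five criteria still stop it at any pain score. The Background section cites work in which enteral naloxone did not impair pain control. Usual pain medication continues, and routine care includes "pain score, and neurological assessment every 1 – 4 hours". All of this stands, and it is why the point is small. It does not remove the gap, because no other written rule covers a patient with high pre-dose pain, worsening pain and two other signs.

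Two further objections also stand. The replacement thresholds have no clinical basis in the documents: the 3-point rise is chosen because it leaves triggers at 1-5 unchanged, so the investigators should set the values. And on 0-100 the suggested wording closes only part of the blocked range.

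A reader might infer more than the documents support:

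- That the stopping rule fails altogether for patients in severe pain. It does not, since the five other criteria still operate, and nothing in the protocol forbids a clinician from stopping the drug.
- That a rise from 0 can never count. The text is ambiguous there, and one natural reading counts any rise.
- That scoring every 1 to 4 hours makes new dose-timed scores a necessary part of the remedy. Whether a score falls within the hour after a dose is a separate, optional question. Adding such scores would also conflict with the Safety Monitoring Plan's statement that monitoring adds no patient burden.

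**Conclusion.** The point holds in a limited form. Criterion 4 cannot be met from a pre-dose score of two-thirds of the scale maximum or more. That cutoff is exact for any bounded scale; only its translation into 7-10 or 67-100 rests on an assumed range. From 0 the criterion is unsettled, not unmeetable.

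The consequence is confined to a patient whose pain worsens and who meets exactly two other criteria. How many patients that is cannot be estimated, because the documents do not give the distribution of pre-dose pain or the frequency of the other signs. The primary outcome, the power and the between-group analysis are not affected. This is a cheap improvement to a safety rule and does not threaten the trial's conclusions.

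**What to change.** Keep three-of-six and the existing 50% rule, and extend criterion 4, for example:

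> Pain score rises from the last pre-dose score by more than 50%; or by at least 3 points on a 0-10 scale (30 on 0-100); or, from a pre-dose score of two-thirds of the maximum or more, by at least 2 points (20 on 0-100) or to the top of the scale. Both readings use the same scale.

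The investigators should set the thresholds and name the scale and its range. With this wording a rise of 3 or more from 0 counts under either reading; a short clause saying whether 1 or 2 points from 0 counts would settle the rest. A patient already at the maximum still relies on the other five criteria. The absolute limbs should be added to the 50% rule and not replace it: a 3-point rise alone would lose the moves 1 to 2, 1 to 3, 2 to 4 and 3 to 5, which now count.

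The cost is a change to one criterion, with no new assessments. The downside is somewhat more discontinuations, mainly at high pre-dose scores, by an amount that the documents do not allow to be estimated. A one-point rise from 9 to 10 would count, as 1 to 2 already does.
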